## 4.5 Work Package 4: The Development of an Evaluation Tool to Assess the Impact of the DSF

We are not aware of any standard instruments for evaluating the quality of ethical decision-making in clinical practice or for evaluating interventions to improve ethical decision making. Further literature review will confirm this and identify any new studies that inform the development of an evaluation tool, or new tools developed that could be used or adapted. Studies of interventions to support ethical decision making have usually used clinicians' views on the effect of the interventions on their practice to evaluate its impact.(98) A randomised controlled trial of ethics case consultation in ICU used the outcome of ICU length of stay to assess effectiveness of the intervention but did not look at the impact on the process of decision making.(99) We will develop an evaluation tool specifically aimed at assessing the impact of interventions to facilitate ethical decision-making that focuses on the decisions and decision-making process rather than secondary outcomes. Within the context of this project we will conduct initial testing for reliability, validity, and responsiveness.

Following our systematic review of evaluation models for ethical decision making to inform the development of our evaluation tool, we will consult with our project lay advisory and stakeholder groups to finalise which model to use. However, we envisage that it will draw on the 'Accountability for Reasonableness' framework (AFR).(100) This is the most commonly used ethical framework for allocation of limited medical resources and focuses on the process of decision making rather than relying on a specific moral theory. AFR has four requirements, decisions must be transparent; based on reasons stakeholders can agree are relevant; revisable in the light of new evidence and arguments; and that there should be an appeals process. Other authors have highlighted the requirement for priority setting decisions by clinicians (including ICU admissions) to be transparent (AFR requirement 1) and ethically justifiable (AFR requirements 2 and 3).(101, 102) Any DSF therefore should improve the transparency and ethical justification of decisions regarding referral and admission to ICU. A further ethical requirement is one of equity, which can be interpreted as consistency of process (the factors taken into account and the process of decision making should be consistent across all patients and all decision makers). If this framework is agreed on, we will develop an evaluation model that examines these three requirements. This evaluation will use both a quantitative and qualitative approach to evaluate the impact of the DSF on the decision-making process. Transparency and a basis in ethical reasons are qualities of the decision-making process that can be operationalised qualitatively as categories.(103) Decisions can then be categorised and a quantitative comparison made before and after the implementation of the decision support tool. Consistency of process across a Trust will be assessed qualitatively.

### 4.5.1 Objectives:

1. To develop a tool to evaluate the impact of the decision support framework
2. To pilot its use and test its reliability, face validity and responsiveness in two NHS Trusts in parallel with the DSF implementation feasibility study.

#### 4.5.2 Setting

Data collection in this work package will take place in a total of five acute NHS trusts. Data collection for the development of the evaluation tool will occur in two trusts that are participating in WP1. Data collection to test the evaluation tool will occur in the three NHS trusts which are taking part in the implementation study (work package 3).

#### 4.5.3 Data collection for categorisation development and testing of evaluation tool

An NHS research nurse will identify the clinical records of a consecutive series of patients where a referral to ICU was received (if referrals are not specifically logged by the unit we will use unplanned or emergency ICU admissions and the records of the critical care outreach team to identify patients referred to ICU). The section of the records relating to the discussion about referral to ICU and any decision made will be copied and any patient identifiers removed.

Data collection will continue until the team have a consistent system for categorisation. The research team will examine the records and categorise them as

- i) Including evidence of transparency or not; and
- ii) Including evidence of ethical reasoning or not.

Examples of evidence of transparency might be: the clinical notes include a clear description of the reasons for the decision; there is a summary of discussion with patient's family; the names of those consulted and their views are recorded. Evidence of ethical reasons might be: the clinical notes include a summary of the likely outcome of admission to ICU based on patient data and relevant evidence; advance directives have been asked about; there is a clearly argued case for the decision referring to relevant reasons. Two researchers will undertake categorisation independently and disagreements in categorisation will be resolved by consensus or by a third assessor where necessary. We will develop the categorisation using the first 10-20 cases. The categorisation will then be applied to a further 10-20 cases and consistency reviewed and categorisation criteria revised. This will continue until consistency of categorisation is achieved and no further revisions are made.(104) The lay advisory group will review and advise on this process.

*Face Validity:* We will use one of our stakeholders meetings to present the evaluation tool and the categorisation developed by the research team. We will ask members to comment on whether they agree that our categorisation criteria are measuring the requirements of transparency and ethical justification in the context of decisions to refer or admit to ICU. Any comments or suggestions will be recorded and if necessary adjustments to the categorisation criteria will be made.

#### 4.5.4 Testing reliability and responsiveness in the feasibility study

In each of the three Trusts participating in the DSF feasibility study, data will be collected from a consecutive sample of 20 cases, using the same method as in data collection for categorisation, in the month prior to implementation of the decision framework. Two months following implementation data collection will be repeated.

*Responsiveness to change:* We will test the responsiveness of the decision tool by assessing the proportion of records categorised as transparent and ethical in the pre and post implementation records. This will be calculated for each category by a t-test of proportions.

*Reliability:* Two assessors, one from the study team and one independent assessor will categorise each decision event identified as i) transparent or not and ii) following ethical reasoning or not using the categorisation framework agreed in the development stage. Inter-rater reliability for each category will be calculated using the kappa statistic, along with its 95% confidence interval.

*Consistency:* Consistency of decision making will be assessed through configurational comparative methods,(105, 106) at this stage of developing the tool, undertaken by hand so subtle inconsistencies are not missed. This involves the comparison of configurations of attributes of cases and their supporting data. The criteria (probably two or three) used for each categorisation of transparency and ethical reasoning will form the attributes (e.g. family members consulted) and there will be data to support the attributes for each case. The data on each attribute (usually one or two sentences from the clinical record or DSF) for each of 120 cases (see sample size below) will be transcribed into a database. Comparative analysis will be undertaken comparing each case with each other case. The comparative analysis will be undertaken independently by two analysis teams and the results compared and discussed. The potential for quantitating this qualitative approach will be explored.(105, 107)

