#### 4.5.5 Sample size calculation:

As this work package pilots the evaluation tool, no prior research hypotheses can be stated and hence no formal sample size calculations can be constructed. Hence, in each of the three Trusts participating in the decision support framework feasibility study, we will simply collect data from a consecutive sample of 20 cases in the month prior to implementation of the decision framework. Two months following implementation, data collection will be repeated. Sixty cases in each sampling period is anticipated to be an achievable number of decisions to scrutinise by the research team and easily obtainable over a month of data collection at most Trusts. Furthermore, assuming that the initial percentage of decisions categorised as transparent (or ethical) lies between 10% - 85%; an overall number of 120 cases (60 in each group) is sufficient to detect a minimum increase of between 14% (if the initial proportion is 85%) and 25% (initial proportion of 40%).

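### The before/after test of responsiveness ignores the Trust strata built into the sampling; stratifying by Trust costs nothing and gains power if Trust baselines differ

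*Protocol*

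**What the plan says.** Protocol section 4.5.4 tests responsiveness by "assessing the proportion of records categorised as transparent and ethical in the pre and post implementation records". Each record is rated yes or no on each of the two categories. The method follows at once: "This will be calculated for each category by a t-test of proportions".

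The sampling is by Trust: "In each of the three Trusts participating in the DSF feasibility study, data will be collected from a consecutive sample of 20 cases" before implementation, repeated two months after it. Section 4.5.5 then treats the material as two groups: "an overall number of 120 cases (60 in each group) is sufficient to detect a minimum increase", of 14 points from a baseline of 85% and 25 points from a baseline of 40%.

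Neither section mentions stratification or adjustment by Trust. Section 4.5 leaves consistency across a Trust to qualitative assessment. Section 4.4.3.2 selects one small, one medium and one large ICU.

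**The concern.** The sample is balanced by Trust, so differences in level between Trusts cancel from the before/after contrast. An unstratified 60 v 60 test still counts those differences as noise in its standard error. If the Trusts document decisions to different standards at baseline, the test rejects too rarely and a responsive tool could look unresponsive. Trusts picked to differ in ICU size make unequal baselines plausible, though the protocol does not say that ICU size affects documentation.

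This is not a detail left open for a later plan: the protocol names the test, and it is the only inferential method given for responsiveness, one of the properties that section 4.5.1 sets out to test.

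**Working it through.** **1. The plan's own figures.** Alpha, sidedness and power are not stated; I assume two-sided 5% and 80%. For two proportions with no Trust term,

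n per group = [1.96·√(2p̄(1−p̄)) + 0.8416·√(p₁(1−p₁)+p₂(1−p₂))]² / (p₂−p₁)².

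- 40% to 65%: p̄ = 0.525; (1.96×0.7062 + 0.8416×0.6837)²/0.0625 = 61.4, so 62.
- 85% to 99%: p̄ = 0.92; (1.96×0.3837 + 0.8416×0.3707)²/0.0196 = 57.8, so 58.

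Solved at n = 60, the detectable increases are 25.3 and 13.9 points. The stated 25% and 14% therefore reproduce from a plain two-sample formula, so the planning ignores Trust as the test does.

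**2. The estimate.** With 20 and 20 per Trust, each Mantel-Haenszel weight is 20×20/40 = 10. The stratified risk difference is then the plain average of the three Trust differences, which equals the pooled 60 v 60 difference. The estimate does not change; only its standard error does.

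**3. The standard error with no change.** With Trust rates pₖ and mean p̄:

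- unstratified: √(2p̄(1−p̄)/60)
- stratified: (1/3)·√(Σ 2pₖ(1−pₖ)/20)

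With p̄ = 0.40 the unstratified value is √(0.48/60) = 0.0894 throughout. For 10/40/70%, Σpₖ(1−pₖ) = 0.09+0.24+0.21 = 0.54, and the stratified value is (1/3)√(1.08/20) = 0.0775. The ratio is 1.155, and the expected type I error is 2Φ(−1.96×1.155) = 2.4%.

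**4. Power.** I simulated 3 × (20 v 20) records with a common log-odds shift of 1.0, comparing the pooled z-test with the Cochran-Mantel-Haenszel (CMH) test without continuity correction. The baselines are assumptions.

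| Trust baselines | Stratified SE | SE ratio | Type I error, pooled / CMH | Power, pooled / CMH | Power lost |
|---|---|---|---|---|---|
| 40/40/40% | 0.0894 | 1.000 | 5.1% / 5.1% | 78.5% / 78.5% | 0 |
| 30/40/50% | 0.0882 | 1.014 | 4.8% / 4.9% | 76.4% / 76.5% | 0.1 |
| 20/40/60% | 0.0843 | 1.061 | 3.9% / 5.0% | 69.4% / 71.6% | 2.2 |
| 10/40/70% | 0.0775 | 1.155 | 2.4% / 5.0% | 52.8% / 63.5% | 10.7 |

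Power falls down the table for both tests partly because the same log-odds shift gives a smaller average change in percentage points. With a constant change of 25 points instead, power is 80/80%, 81/81%, 82/84% and 84/90%, so the widest spread costs about 6 points.

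**5. t versus z.** For 24/60 v 39/60, t = 2.81 (p = 0.0058) and z = 2.74 (p = 0.0061). Simulated rejection rates differ by less than 0.1 point.

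**6. Few failures at the top of the range.** At 85% v 99% the expected number of negative ratings is (9 + 0.6)/2 = 4.8 per period. Exact enumeration at 60 v 60 gives the pooled z-test a true type I error of 4.7%, 5.0%, 5.0% and 4.6% at common proportions of 0.85, 0.90, 0.92 and 0.95. Its exact power for 85% v 99% is 88.7%. Fisher's test has 77.1%, with a true size of 1.8% at 0.92.

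**7. A change that varies by Trust.** With all baselines at 40%, no average change and an assumed between-Trust SD of the change of 0.05, 0.10 or 0.15, the unstratified test's type I error is about 6%, 10% or 16%.

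**The case against.** The case for leaving the sentence alone is substantial. The loss depends on spreads that the protocol does not give, and it is negligible unless Trusts differ widely. ICU size does not establish different documentation practice. Under a common effect the error is in the conservative direction. Section 4.5.5 says that no prior hypotheses can be stated, and DSF feasibility is judged on the separate criteria of section 4.4.4.4. All of this stands, and it keeps the severity down. It does not favour the unstratified test, because stratifying cost nothing even when the baselines were identical.

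A reader might also infer stronger points that the documents do not support:

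- *That a t-test on yes/no data invalidates the result.* The name is loose, but at 60 v 60 the choice between t and z is immaterial.
- *That the standard error is simply wrong.* It is too large only if baselines differ, and the difference it accompanies is not confounded by Trust.
- *That sparse counts at 85% to 99% call for an exact test.* The pooled z-test holds its level there, and Fisher's test would lose power.
- *That only a p-value will be reported.* Section 4.5.4 has both proportions assessed, so the change is available. A confidence interval could properly be left to an analysis plan that is not shown.

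**Conclusion.** The point holds as a free improvement of low to moderate severity. The protocol fixes an unstratified test for a sample that it has balanced within three Trusts. If baselines differ, that test is conservative: from no loss at equal baselines to about 11 points of power at 10/40/70%, with type I error falling from 5.0% to 2.4%. These sizes rest on assumed Trust rates, a common log-odds shift of 1.0 and a two-sided 5% level.

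It would go too far to call the unstratified test always conservative, or stratification a full remedy. Section 4.4.3.4 lets each Trust's champions choose how to introduce the framework, so the change itself may vary by Trust. The unstratified test can then reject too often. CMH, which tests a common effect, does not cure this, and three Trusts are too few to estimate such variation reliably.

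**What to change.** In section 4.5.4, replace the sentence that names the test with:

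> For each category, the change in proportion will be estimated as a Mantel-Haenszel risk difference stratified by Trust with 95% confidence interval, and tested with a Cochran-Mantel-Haenszel test stratified by Trust without continuity correction; Trust-specific proportions before and after will also be shown.

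Do not add an exact-test clause for small expected counts. The Trust-specific proportions let a reader see whether the change was similar across Trusts, which the stratified test cannot settle.

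The cost is one sentence of wording. Sampling is already by Trust, so no further records, sites or patients are needed, and the sample size in section 4.5.5 can stay as it is.

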#### **4.4 Work Package 3: The development of a Decision Support Framework (DSF) and the testing of its implementation**

Analysis of preceding work packages will inform the development of a decision support framework (DSF) to facilitate the process of decision-making regarding whether an individual patient is or is not admitted to ICU. The DSF will provide a framework to support consistent, transparent and ethically justifiable patient centred decision-making through prompting consideration; of relevant factors identified in the previous work packages. It is not intended to determine whether an individual patient should or should not be admitted to ICU. If considered appropriate, it will provide links to relevant guidance, evidence and statistical calculations. It will support the referring team to deliver a quality referral that takes into account all relevant details, and ensure all details are available to the decision-making individual or team. It will also provide a mechanism for documentation hence audit of the decision-making process including factors taken into account by the decision maker.

The specifics of its format and content will be dependent on the findings that emerge from the first two work packages, but given the current NHS policy for hospitals to become paperless by 2018 the DSF will need to be developed in a format that has the potential to be hosted on servers at individual trusts or accessed through the NHS net (noting patient confidentiality issues). It will be designed and tested in versions intended for referring as well as receiving clinicians based upon relevant evidence and values. In addition, in order to be practicable in routine care across the NHS it will be designed to be adaptable to varied contextual factors, such as organisational settings, patient presentation, times of day, and availability of ICU resources. We will develop associated education and support materials to facilitate its implementation in individual Trusts.

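### Nothing in the plan masks the period when the pre- and post-DSF records are rated, so rater expectation could inflate the responsiveness result by an unknown amount

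*Protocol*

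**What the plan says.** Section 4.5.4 takes 20 consecutive cases in each of three Trusts in the month before implementation and repeats the collection two months after. That gives 60 records per period and 120 in all.

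- Raters: "Two assessors, one from the study team and one independent assessor will categorise each decision event identified as i) transparent or not", and likewise for ethical reasoning, using the framework agreed in the development stage.
- Outcome: responsiveness is judged by "assessing the proportion of records categorised as transparent and ethical in the pre and post implementation records".
- Test: "This will be calculated for each category by a t-test of proportions".
- Preparation of the material (section 4.5.3, whose method 4.5.4 adopts): the relevant part of the record "will be copied and any patient identifiers removed". Section 4.5.6 adds that the research nurse extracts the information and passes it on in anonymised form.
- Criteria (examples in 4.5.3): for transparency, that "the clinical notes include a clear description of the reasons for the decision"; for ethical reasons, among others, a clearly argued case for the decision.
- The DSF (section 4.4): "It will also provide a mechanism for documentation hence audit of the decision-making process including factors taken into account by the decision maker". The Consistency paragraph of 4.5.4 describes the supporting data as "usually one or two sentences from the clinical record or DSF".

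No section provides for masking the assessors to period, pooling the two sets of records, rating in random order, or presenting them in one format.

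**The concern.** A before-and-after comparison of ratings is fair only if the same standard is applied to both sets. Here the standard involves judgement (is a description clear, is a case clearly argued). One rater has an interest in the outcome: section 4.4.2 has the research team write the clinical and ethical content of the DSF, and section 4.5.3 has it develop the categorisation. If raters can tell which records come after implementation, they may read borderline ones more generously.

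This matters because the pre/post difference is the only test of responsiveness in 4.5.4. Responsiveness is one of the properties that section 4.5.1 sets out to test, and section 7 lists the evaluation tool among the key outputs. A tool that appeared responsive because of how it was applied would carry that overstatement into later use.

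**Working it through.** **Can the period be recognised?** The DSF exists only after implementation. Section 4.4 makes it a place where the decision is documented, and the Consistency paragraph of 4.5.4 names it as a source of case data. Material from a record made with the DSF will therefore probably show its period. This is an inference: the rating paragraph itself does not say that DSF pages are shown. It also need not apply to every post record, since the success criterion in 4.4.4.4 is use in more than 50% of eligible patients. Dates could also reveal the period. The protocol says neither that they are removed nor that they are kept.

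**The plan's own figures.** Section 4.5.5 gives 60 per period as enough to detect a rise of 14 points from 85% or 25 points from 40%. It states no significance level or power. Assume two-sided 5% and 80%, and use

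n = [1.96·√(2p̄(1−p̄)) + 0.84·√(p₁(1−p₁)+p₂(1−p₂))]² / (p₂−p₁)².

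- 85% to 99%: 58 per period.
- 40% to 65%: 62 per period.

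Both are close to 60, so the stated figures reproduce. Masking does not change them.

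**How few re-rated records would matter?** With a pooled two-proportion z-test at 60 v 60, the smallest significant rises are:

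- from 6 to 15 records (10% baseline): 9 records, z = 2.16;
- from 24 to 35 (40% baseline): 11 records, z = 2.01;
- from 51 to 58 (85% baseline): 7 records, z = 2.21.

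**Illustration with no true change.** Let p be the true proportion in both periods, and L the share of otherwise negative post records that raters upgrade. L is an assumption; the protocol gives no figure for it. The baselines are taken from the 10% to 85% range in 4.5.5.

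- Observed post proportion: q = p + (1−p)L.
- Standard error: SE = √{[p(1−p)+q(1−q)]/60}.
- Chance of a significant result: Φ((q−p)/SE − 1.96) + Φ(−(q−p)/SE − 1.96).

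| p | L | q | (q−p)/SE | chance |
|---|---|---|---|---|
| 10% | 10% | 19% | 0.090/0.0638 = 1.41 | 29% |
| 10% | 20% | 28% | 0.180/0.0697 = 2.58 | 73% |
| 40% | 10% | 46% | 0.060/0.0902 = 0.67 | 10% |
| 40% | 20% | 52% | 0.120/0.0903 = 1.33 | 26% |
| 85% | 10% | 86.5% | 0.015/0.0638 = 0.24 | 6% |
| 85% | 20% | 88% | 0.030/0.0623 = 0.48 | 8% |

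With L = 0 the chance is 5%. Exact binomial enumeration of the pooled z-test gives nearly the same values (for example 73% and 28% at the 10% baseline, 27% and 11% at 40%).

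**If only DSF-bearing records are affected.** Suppose half of the negative post records carry the DSF and L = 20% applies to those alone. The effective L is 0.5 × 20% = 10%, so the 20% rows fall to the 10% rows: 29%, 10% and 6%.

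**Would kappa show it?** Kappa measures agreement between the two assessors. If both are more generous to post records, they still agree, and kappa stays high while the pre/post difference is biased.

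**The case against.** The protocol does not prescribe unmasked rating; it is silent. Removal of dates, rating order and format could be set in a rating manual. That is fair as far as it goes, and a reader should not infer that dates and the DSF layout are known to stay visible in every post record. But sections 4.5.3 and 4.5.4 do fix who rates, what is rated, what is removed and how the result is tested. Masking belongs with those items and must be settled before rating begins.

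There are safeguards: one assessor is independent, and both apply criteria agreed beforehand. These narrow the room for drift. Neither prevents a rater from knowing the period, and the criteria still require judgement.

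A stronger reading is tempting: that the mere presence of the DSF form could produce the result. The documents do not support it. Most of the example criteria in 4.5.3 need case-specific content that a blank or ticked template would not supply. Better documentation is also part of what the DSF is for (section 4.4), and section 4.5 expects a DSF to improve transparency. A rise because clinicians wrote more is the change that the tool is meant to detect. Only a shift in the raters' standard is bias.

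A reader might also take 73% as the expected error rate. It is the highest cell in the table, from an assumed 20% upgrading at the lowest baseline. At 85% the same assumption gives 8%.

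Finally, section 4.5.5 describes this as a pilot of the tool without prior hypotheses, and no feasibility criterion in 4.4.4.4 depends on the test. That limits the consequence.

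**Conclusion.** The point stands as a design weakness that is cheap to correct. Nothing in the protocol masks the period or mixes the records, one rater comes from the team that produces both the DSF and the tool, and the criteria are subjective. Rater expectation could therefore inflate the only test of responsiveness, and kappa would not reveal an expectation that both raters share.

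The size cannot be known from the documents. It ranges from almost nothing at a high baseline to a serious distortion at a low one, and depends on the assumed upgrading share, on two-sided 5% testing, and on post records being recognisable. The last is probable where the DSF was used but is not stated. The consequence is a possible overstatement of the tool's responsiveness in a pilot. It does not affect the sample size or patient care.

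**What to change.** Amend 4.5.3 and 4.5.4 before rating of the feasibility records starts:

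1. The research nurse, who already extracts and anonymises the text, also removes dates and Trust names and supplies every extract in one common typed format without the DSF layout.
2. The 120 records from both periods are pooled and rated in random order.
3. The report states that masking was partial. Optionally, raters guess the period of each record and the share of correct guesses is reported.
4. The text says that better documentation prompted by the DSF counts as an intended effect, not as rater bias. Whether a ticked item without case-specific content is evidence of transparency or ethical reasoning is decided when the categorisation criteria are developed.

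Cost: some typing time, reduced by the fact that 4.5.4 already has short extracts for 120 cases transcribed. Masking will remain incomplete, because wording prompted by the DSF may still be recognisable. The sample size is unchanged.

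### Kappa is the only planned measure of assessor agreement and the records it uses are not stated; at the extremes of the protocol's own range it can understate agreement

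*Protocol*

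**What the plan says.** Reliability is one of the three properties of the tool that protocol section 4.5.1 sets out to test, with face validity and responsiveness. Section 4.5.4 gives the design: "Two assessors, one from the study team and one independent assessor will categorise each decision event identified as i) transparent or not", with a second yes/no rating for ethical reasoning. The analysis is then stated in one sentence: "Inter-rater reliability for each category will be calculated using the kappa statistic, along with its 95% confidence interval". No other agreement measure is named, no kappa value is set as acceptable, and the records to be used (all 120, or each period of 60) are not stated.

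Section 4.5.5 gives the range over which the tool is expected to work, "assuming that the initial percentage of decisions categorised as transparent (or ethical) lies between 10% - 85"%. The detectable increases with 60 records per period are given as "14% (if the initial proportion is 85%) and 25% (initial proportion of 40"%). In absolute terms that is 85% to 99% and 40% to 65%. Section 4.5 states the expected direction: "Any DSF therefore should improve the transparency and ethical justification of decisions regarding referral and admission to ICU".

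Section 4.5.3 describes an earlier check while the categories are being developed: "This will continue until consistency of categorisation is achieved and no further revisions are made". It names no statistic and, under section 4.5.2, takes place in two other Trusts.

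**The concern.** Kappa compares observed agreement with the agreement expected by chance from the two assessors' marginal rates. When most records fall in one category, chance agreement is already high and little room is left above it. A few disagreements then pull kappa down sharply, although the assessors agree almost always. The same quality of rating therefore gives different kappas depending on how common the category is.

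The protocol's planning range reaches both ends of this scale, and the DSF is meant to change the rate between the two periods. With kappa alone, a reader cannot separate how well two assessors agree from how common transparent or ethically reasoned records happened to be. The 95% interval does not help, because it describes sampling error and not dependence on prevalence. The tool is a listed project output (section 7), so its reliability figure would follow it into later use.

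**Working it through.** **1. The plan's own figures.** Section 4.5.5 states neither significance level nor power, so I assume 5% two-sided and 80%, without continuity correction. With n per group = [1.96·√(2p̄q̄) + 0.8416·√(p₁q₁ + p₂q₂)]² / (p₂ − p₁)²:
- 85% to 99%: (1.96·√0.1472 + 0.8416·√0.1374)² / 0.14² = 57.8, so 58 per group. Power at 60 per group is 0.815.
- 40% to 65%: (1.96·√0.49875 + 0.8416·√0.4675)² / 0.25² = 61.4, so 62 per group. Power at 60 per group is 0.790.

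Both figures reproduce closely, so 85% to 99% is a scenario the plan itself uses. No kappa target or precision is stated, so there is none to reproduce.

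**2. Kappa for raters of fixed accuracy.** Assume two raters, independent given the truth, each with sensitivity = specificity = a. The protocol gives no value for a; I use 0.95, with 0.90 and 0.98 as a range. For true proportion positive p:
- observed agreement Po = a² + (1 − a)², which does not depend on p: 0.820, 0.905 and 0.961 for a = 0.90, 0.95 and 0.98
- proportion rated positive m = a·p + (1 − a)(1 − p)
- chance agreement Pe = m² + (1 − m)²
- kappa = (Po − Pe) / (1 − Pe)

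| p | m (a = 0.95) | Pe (a = 0.95) | kappa, a = 0.95 | a = 0.90 | a = 0.98 |
|---|---|---|---|---|---|
| 10% | 0.140 | 0.759 | 0.61 | 0.39 | 0.81 |
| 40% | 0.410 | 0.516 | 0.80 | 0.63 | 0.92 |
| 65% | 0.635 | 0.536 | 0.80 | 0.62 | 0.91 |
| 85% | 0.815 | 0.698 | 0.68 | 0.48 | 0.86 |
| 92% (85% and 99% pooled equally) | 0.878 | 0.786 | 0.56 | 0.34 | 0.78 |

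At 10%, for example, (0.905 − 0.7592) / (1 − 0.7592) = 0.1458 / 0.2408 = 0.61. In 10,000 simulated sets of 120 records with 85% and 99% pooled and a = 0.95, median kappa was 0.55 with a 95% range of 0.30 to 0.77.

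**3. One period of 60 records, nearly all rated positive, with no assumption about accuracy.**
- Each assessor marks one record negative, and not the same one: Po = 58/60 = 96.7%. Pe = (59/60)² + (1/60)² = 0.9672. Kappa = (0.9667 − 0.9672) / (1 − 0.9672) = −0.02.
- One assessor marks a single record negative and the other none: Po = Pe = 59/60 = 98.3%, so kappa = 0.
- Both rate all 60 positive: Po = Pe = 1, so kappa is undefined.
- For contrast, two disagreements in 60 with an even split (29 both positive, 29 both negative, one each way): Po = 96.7%, Pe = 0.50, kappa = 0.93.

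In the first case positive agreement is 2·58 / (2·58 + 2) = 98.3% and negative agreement is 0 / (0 + 2) = 0%. That shows the actual position: the assessors agree on positives, and there is almost no information about negatives.

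**4. Low and middle baselines (a = 0.95).** From 40% to 65%, kappa is 0.80 in both periods. From 10% to 30%, it rises from 0.61 to 0.78 (m = 0.32, Pe = 0.5648, 0.3402 / 0.4352). Pooled at 20% it is 0.73 (m = 0.23, Pe = 0.6458, 0.2592 / 0.3542).

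**The case against.** A reader might infer that a DSF that works would make an accurate tool look unreliable. The protocol does not support that as a general statement.

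- From low or middle baselines, which section 4.5.5 includes, success moves the rate towards the middle and kappa holds or rises (step 4).
- At the top of the range, kappa pooled over 120 records is reduced to about 0.56 and does not collapse. Values near zero need the later 60 records analysed alone at a very high rate, and section 4.5.4 does not say that this will be done.
- 99% is the upper end of a detectability statement and not a forecast; section 4.5.5 says no hypotheses can be stated. The success criterion in section 4.4.4.4 is DSF use in over 50% of eligible patients. With an 85% baseline, 50% use and every DSF record rated positive, the later rate is 0.5·85% + 0.5·100% = 92.5%. The same rater model then gives kappa 0.54 for that period: low for 90.5% agreement, but not zero.
- Putting 99% into the rater model as the true rate gives kappa 0.14, but this should not be read as the protocol's scenario. Section 4.5.5 speaks of records as categorised, and 95% accurate raters would categorise only 0.95·0.99 + 0.05·0.01 = 94.1% as positive. The 2×2 tables in step 3 avoid this difficulty.
- No threshold or pass/fail rule is attached to kappa, so nothing in the plan would declare the tool unreliable.

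All of this stands, and it limits the point to the extremes of the range. It can also be said that kappa with a 95% interval is conventional for two raters and a yes/no category, and that a statistical analysis plan, not shown, could add measures. But the protocol itself names the reliability measure and names only this one. The absence of a threshold does not help either: a lone kappa of 0.5 would be reported without the context needed to read it.

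**Conclusion.** The point holds as a limit on interpretation. With kappa as the sole measure and the set of records unstated, the reliability result could understate assessor agreement at either end of the planned range. At an assumed 95% accuracy, 90.5% agreement gives kappa 0.80 at 40%, 0.61 at 10% and about 0.56 for 85% and 99% pooled; the pooled figure runs from 0.34 to 0.78 for 90% to 98% accuracy. On one period of 60 records rated almost all positive, kappa can be near zero or undefined with more than 95% agreement.

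The figures from the rater model rest on assumed accuracy, equal sensitivity and specificity, and independence of the raters given the truth; they also take the protocol's percentages as true rates. The 60-record examples rest on none of these. In the middle of the range kappa behaves well. The protocol does not support a claim that success of the DSF will in itself make the tool appear unreliable.

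**What to change.** In section 4.5.4, state that kappa with its 95% interval will be reported for all 120 records and for each period separately, for each of the two categories. Beside each kappa, give overall agreement, positive agreement and negative agreement with 95% intervals. State that the reliability conclusion will rest on these together, and that kappa will be reported as not estimable if both assessors place every record in one category.

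This uses the same ratings, with no further assessor or records. The cost is a few more reported figures. When few records are rated negative, the interval for negative agreement will be wide, which correctly shows how little the data say about agreement on negatives.
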